### XI.2 Provide the rationale or power analysis to support the number of subjects proposed to complete this study.

Sample size calculations. Sample sizes were calculated based on 80% power at an alpha level of 0.05. Estimated effect sizes for Aim 1 were used for final sample size calculation for obese prediabetic subjects because carotid-femoral PWV is the primary outcome and has the smallest effect size (d) in pilot data of 4 days before vs. after Salsalate. A sample size of 16 subjects per group was determined based on the d of 1.06, based on mean difference in carotid-femoral PWV (-1.0  $\pm$  1.0 m/sec) after Salsalate vs. Placebo.

With a conservative estimated attrition rate of 15-20% and the 2:1 randomization, a total of 20 subjects will be assigned to the Salsalate group, and 10 subjects to the placebo group was determined to be required for the study (total sample size=30). A

sample size of 12 for Aim 2 (FMD) was determined from d of 1.2 for a mean difference in FMD of  $\pm$  2.2 after 4 days Salsalate vs placebo based on previously published work by the PI (19). Because the effect sizes for Aim 1 and 2 are based on preliminary data of 4 days of Salsalate treatment and our proposed study is 4 weeks, we predict that the actual effect sizes will be slight higher because of the longer duration of treatment. Therefore, the proposed study will help determine actual effect sizes for chronic Salsalate therapy for a future larger randomized clinical trial.

A total of 10 obese non-prediabetic control subjects will be recruited to established differences in main outcomes at baseline but will NOT undergo randomization or salsalate/placebo treatment period.

Therefore, total sample size to be enrolled is 40.

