**Hypothesis 1:** Chronic inflammation inhibition will improve microvascular and large elastic artery function in obese adults with prediabetes.

**Aim 2:** To measure muscle sympathetic nervous system activity (MSNA) and baroreflex sensitivity in obese prediabetic adults before and after 1 month of salsalate or placebo.

**Hypothesis 2:** Chronic inflammation inhibition will decrease MSNA and improve baroreflex sensitivity in obese adults with prediabetes.

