### VII.E.1 Will subjects be randomized? Yes

VII.E.1.a Will any subjects be blinded to which study arm they have been assigned?

Yes

VII.E.1.b Does the protocol permit telling subjects their treatment assignment at the end of the entire study?

Yes

VII.E.1.c Describe the circumstances under which subjects will be told what study arm they have been assigned.

At the end of the study, or after an adverse event that the subject is withdrawn from the study.

VII.E.2 Describe randomization scheme/assignment including ratio such as 1:1, 2:1 etc.

Subjects will be randomized 2:1 to salsalate or placebo, respectively so their is 2/3 chance they will be randomized to salsalate and 1/3 to placebo. This scheme was chosen to ensure proper effect sizes can be determined in the salsalate group in this pilot study. The obese non-prediabetc group will not be randomized and only undergo baseline testing.

VII.E.3 Will any questionnaires, surveys, or written assessments be used to obtain data directly from subjects in this study?

Yes

VII.E.4 List all questionnaires, surveys, written assessments and ATTACH each one to the application. (NOTE: You are NOT prohibited from attaching copyrighted materials to this application)

Phone screening questionnaire
Demographics and Contact Info questionnaire
Health History questionnaire
Modifiable Activity Questionnaire (MAQ)

3 Day dietary record (CRU bionutrition)

Salsalate screening log

VII.E.5 Does this project involve creating any audiotapes, videotapes, or photographs?

No

VII.E.6 Provide a detailed description in sequential order of the study procedures following the consent process - DO NOT cut and paste from the Consent Document.

Describe study populations separately if they will be participating in different procedures - include CONTROL population if applicable.

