### XI. Data Analysis

### XI.1 Describe the analysis methods you will use, including, if applicable, the variables you will analyze

Statistical analyses. To determine if differences in outcomes are present at baseline between obese pre-diabetic vs. non-pre-diabetic groups, an independent two-sample t-test will be performed. To determine if baseline (pre-intervention) differences exist between salsalate and placebo prediabetic groups after randomization, independent two-sample t-tests will be performed. To test the main hypotheses, a repeated measures ANOVA will be performed in which treatment (salsalate vs. placebo) is the between-subjects factor, and time (pre- vs. post-intervention outcomes) is the within-subjects factor for the primary dependent variables. The critical test for the dependent variable will be the interaction between the within-subjects and betweensubjects factors. Tests for mean contrasts will be used to compare variables of interest pre vs. post Salsalate or placebo. Based on a previous study, we expect small reductions in fasting glucose, triglycerides, LDL cholesterol and possibly systolic blood pressure after Salsalate treatment. Covariates (e.g., variables that change after Salsalate) will be included into the mixed model. Bivariate pearson correlation analysis will be performed on the change in each dependent variable and aforementioned selected covariates after Salsalate.

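### XI.2 states 80% power from 16 subjects per group, but 2:1 randomisation of 30 with 15-20% attrition gives about 65-69% for carotid-femoral PWV

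*Combined protocol and SAP*

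**What the plan says.** XI.2 sets the operating characteristics: "Sample sizes were calculated based on 80% power at an alpha level of 0.05". It names carotid-femoral PWV as the primary outcome and bases the size of the prediabetic cohort on it: "A sample size of 16 subjects per group was determined based on the d of 1.06".

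The next paragraph moves from that figure to the enrolled numbers. It brings in two adjustments: "With a conservative estimated attrition rate of 15-20% and the 2:1 randomization". The arm sizes that come out of this step are given as follows: "a total of 20 subjects will be assigned to the Salsalate group, and 10 subjects to the placebo group". That makes 30 in all, presented as what the study requires. Power is not restated for unequal arms.

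XI.1 specifies a repeated measures ANOVA with treatment between subjects and time (pre, post) within subjects. On which term decides the hypothesis it says: "The critical test for the dependent variable will be the interaction".

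VII.E.2 gives the reason for 2:1: "This scheme was chosen to ensure proper effect sizes can be determined in the salsalate group in this pilot study".

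XI.2 also sizes a second outcome, flow-mediated dilation (FMD): "sample size of 12 for Aim 2 (FMD) was determined from d of 1.2". In I.5, however, Aim 2 reads: "To measure muscle sympathetic nervous system activity (MSNA) and baroreflex sensitivity in obese prediabetic adults". FMD is not part of that aim.

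**The concern.** The calculation yields two equal arms of 16, or 32 evaluable subjects. The enrolment plan protects that number in the salsalate arm only. Placebo starts at 10, below 16 before anyone drops out. Because the decisive test compares the arms, its precision depends on both arm sizes, and mostly on the smaller one.

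XI.2 says the study will supply effect sizes for a larger randomised trial. Someone who reads 80% power and then sees a non-significant PWV interaction would put the chance of having missed the assumed effect at 20%, when it is nearer 31-35%.

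**Working it through.** **Inputs.** From XI.2: alpha 0.05, power 80%, d = 1.06, 16 per group, attrition 15-20%, 20 salsalate and 10 placebo. From XI.1: the test is the treatment-by-time interaction. With two arms and two time points, this is equivalent to a two-sample t-test on change scores. Assumed here: two-sided alpha, equal variances, the same attrition in both arms, analysis of completers, no covariates.

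**Step 1: reproduce the plan's figure.** The normal approximation gives n per arm = 2(1.960 + 0.842)² / 1.06² = 13.97, so 14. The exact noncentral t needs 15 per arm (80.0%), and 16 per arm gives 82.7%. A one-sided test would need 12 per arm and a paired pre-post test 10 subjects. A two-sided, equal-arm, between-group calculation is therefore the closest match to 16.

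**Step 2: completers.**
- Salsalate: 20 × 0.80 = 16; 20 × 0.85 = 17.
- Placebo: 10 × 0.80 = 8; 10 × 0.85 = 8.5, so 8 or 9.
- Total: 24 to 26, against 32 derived.

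**Step 3: power at those numbers.** Noncentrality λ = d × √(n₁n₂/(n₁+n₂)), with n₁+n₂−2 degrees of freedom. For example, 16 v 8 gives λ = 1.06 × √(128/24) = 2.448. The equal-arm equivalent is 2n₁n₂/(n₁+n₂).

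| Salsalate v placebo | λ at d = 1.06 | Equal-arm equivalent n | Power, d = 1.06 | Power, d = 1.00 | d for 80% power |
|---|---|---|---|---|---|
| 16 v 16 (as derived) | 2.998 | 16 | 82.7% | 78.1% | – |
| 20 v 10 (no attrition) | 2.737 | 13.3 | 75.2% | 70.3% | 1.12 |
| 17 v 9 | 2.571 | 11.8 | 69.4% | 64.4% | 1.20 |
| 16 v 9 | 2.544 | 11.5 | 68.3% | 63.3% | 1.22 |
| 17 v 8 | 2.472 | 10.9 | 65.8% | 60.8% | 1.25 |
| 16 v 8 | 2.448 | 10.7 | 64.8% | 59.8% | 1.27 |

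The d = 1.00 column is a sensitivity check. XI.2 prints the PWV difference as −1.0 ± 1.0 m/sec, which gives d = 1.0 if the second figure is the SD. The value 1.06 could come from unrounded data.

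Simulation at d = 1.06 (200,000 replicates) agrees: 82.8% (16 v 16), 75.3% (20 v 10), 69.6% (17 v 9), 64.7% (16 v 8).

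**Step 4: other conventions at d = 1.06.** The normal approximation gives 78.1% for 20 v 10 and 68.7-73.0% for 16 v 8 to 17 v 9. One-sided alpha 0.05 with the exact t gives 84.7% and 76.6-80.3% respectively.

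**Step 5: FMD at d = 1.2.** Taking 12 as a per-group figure, which XI.2 does not spell out, 12 v 12 gives 80.2% two-sided. Under the stated attrition, power is 75.4% (16 v 8) to 79.8% (17 v 9).

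**The case against.** The best defence is that this is a pilot with a deliberate 2:1 ratio, chosen to estimate effects in the salsalate arm. XI.2 also expects somewhat larger effects after 4 weeks than in the 4-day data, and calls its attrition estimate conservative. With no dropout the shortfall is modest, and d = 1.12 would restore 80%. This is enough to defend the design. It does not support the power statement, because estimation in one arm does not give a between-arm test 80% power. The larger effect is not quantified, and under the stated attrition d would have to be about 14-20% above 1.06 (1.204/1.06 = 1.136; 1.269/1.06 = 1.197).

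Sidedness is not stated, and a one-sided test would come close to 80%. This is a fair caveat, but the plan's own figures fit two-sided testing better: 15 per group gives 80.0% at d = 1.06, and 12 per group gives 80.2% at d = 1.2. One-sided testing would need 12 and 10.

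The effect size is itself uncertain. XI.2 describes the pilot data both as before versus after salsalate and as salsalate versus placebo, and the printed mean and spread suggest 1.0. The documents cannot settle which basis was used, so any corrected power must be stated as conditional on d = 1.06. A value of 1.0 would lower power further.

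The upper end of the range also rounds 8.5 placebo completers up to 9.

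**Conclusion.** The concern holds. The 80% power statement in XI.2 belongs to two arms of 16, which the trial will not have. At the plan's own d of 1.06, with two-sided alpha 0.05 and 15-20% attrition, power for the primary PWV comparison is about 65-69%, and 75.2% if nobody drops out. Detectable d at 80% power is about 1.20-1.27 with attrition and 1.12 without.

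The result rests on two-sided testing and on reading d as the standardised between-arm difference in change. It affects how the trial's power is described and how a null result is read. It does not invalidate the pilot. The aim label on the FMD sentence is a separate clerical slip.

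**What to change.** In XI.2, replace the statement of 16 per group at 80% power with wording such as:

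> With 30 subjects randomised 2:1 and 15-20% attrition (16-17 salsalate and 8-9 placebo completers), the two-sided 5% test of carotid-femoral PWV has about 65-69% power at d = 1.06, and 80% power for d of about 1.20-1.27.

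State the sidedness of alpha. Say how d = 1.06 was obtained from the printed mean and spread. Correct the aim label on the FMD sentence, and give FMD power at d = 1.2 as about 75-80% under the same attrition.

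The cost is a rewording of one section and a less favourable stated power. Participants, arms, allocation and analysis are unchanged.

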Forearm blood flow test: There is a risk of mild discomfort on the forearm and wrist when the blood pressure cuffs are inflated. This feeling is completely reversed within several minutes after the cuff is released with no permanent discomfort. There is a small risk of lightheaded or fainting in response to local lidocaine. There is a small risk of bruising at the sight of needle insertion a very small risk of permanent nerve damage or damage to the artery.

Microneurography: Approximately 7% of subjects experience minor tingling in the leg, foot or arm for a few days after the study, but these symptoms have been transient.

Retinal (eye) assessment: The flashes produced by the retinal imagining can be bright and the aftereffects can last several minutes at most.

Risks of drugs to be used in the study.

Salsalate. The most common side effects from the Salsalate medication include (in order of decreasing frequency) tinnitus ('rininging in the ears'), nausea, mild hearing impairment, rash, and vertigo in two studies with combined 280 subjects (percentages not available). Another study of 782 patients with osteoarthritis or rheumatoid arthritis were treated with about 3000 mg/day for 3 weeks, 324 (41%) experience one or more side effects with 234 (30%) requiring discontinuation of Salsalate for GI side effects (13.2%), tinnitus (6.7%), dizziness (1.7%) and 8.5% for other reasons.

Several small trials and one large multicenter clinical trial have been conducted using Salsalate in the dose and duration similar to the proposed dose and duration in this study. In one study of 20 obese middle-aged adults treated for 4 weeks with 4 g/day of Salsalate, 3 subjects required dose reduction of 500 mg due to tinnitus, headache, or dizziness(35). Subjects subsequently had stepped reductions of 500 mg titrated to maximal tolerable dose without symptoms, two tolerated 3.5 g/day and the other tolerated 3.0 g/day and both subjects completed the study. Mean serum salicylate concentrations at 4 weeks were 17.1 mg/dl (in therapeutic range 10-30 mg/dl). Three subjects were withdrawn from the study due to rash, but none had changes in serum measures of renal, electrolytes, anion gap or liver function.

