A recent multicenter trial (Golfine A, et al., Ann Intern Med 2010) Targeting Inflammation Using Salsalate in Type 2 Diabetes (TINSAL-T2D; NCT00392678), 108 patients with type 2 diabetes were randomly assigned to placebo, 3.0, 3.5, or 4.0 g/day for 14 weeks with the primary endpoint being reduction in HbA1c (83). In this longer duration study (compared to our study), about 19-22% of subjects reported tinnitus, one with baseline tinnitus withdrew and 3 patients required dosage reduction but who completed the study. Although there were no serious adverse events, 22-30% of patients experienced hypoglycemia. However, these patients were also receiving concurrent anti-glycemic sulfonylurea therapy for glycemic control. There was also a small trend for an increase in urinary albumin and the 3.5 g/day group showed a small increase in serum creatinine concentration, but no changes in liver function or anion gap. Mild GI symptoms (heartburn, nausea, vomiting, diarrhea) were slightly more common in Salsalate than placebo groups, but there was no episodes of GI bleeding and no subjects required reductions in Salsalate dose. A follow-up multicenter trial (TINSAL-T2D II) is currently underway investigsting the effects to 3.5 g/day of Salsalate on HbA1c for 1 year in patients with type 2 diabetes (NCT00799643). Lastly, in previous study by the PI using high dose Salsalate (4.5 q/day) for 4 days in healthy obese middle-aged/older adults, 2 out of the 17 subjects during the Salsalate treatment withdrew from the study due to dizziness (n=1) and tinnitus (n=1), but neither subject had serum concentrations in the toxic range (19).

Metabolic acidosis: There is a very small risk of metabolic acidosis from salicylate toxicity although none of the above clinical trials above reported any incidence of this. This usually can be treated by stopping salsalate medication and with IV fluid and electrolyte therapy.

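### XI.2 calls an unsourced 15-20% attrition conservative, but the salsalate arm of 20 has no margin beyond 20% loss and the largest study the plan cites had 30% stopping the drug

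*Combined protocol and SAP*

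**What the plan says.** Section XI.2 sets the design target: "Sample sizes were calculated based on 80% power at an alpha level of 0.05". It continues: "A sample size of 16 subjects per group was determined based on the d of 1.06", an effect size "based on mean difference in carotid-femoral PWV" of -1.0 ± 1.0 m/sec. The step from that target to the numbers randomized is one sentence. It opens "With a conservative estimated attrition rate of 15-20% and the 2:1 randomization" and concludes that "a total of 20 subjects will be assigned to the Salsalate group, and 10 subjects to the placebo group". One rate is given for both arms, and no study is cited for it.

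The evidence on tolerability is in section VIII.1, under the risks of salsalate:

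- **Largest study:** 782 patients with osteoarthritis or rheumatoid arthritis on about 3000 mg/day for 3 weeks, of whom "324 (41%) experience one or more side effects with 234 (30%) requiring discontinuation of Salsalate".
- **Twenty obese adults** on 4 g/day for 4 weeks: "Three subjects were withdrawn from the study due to rash".
- **The investigator's own study** at 4.5 g/day for 4 days: "2 out of the 17 subjects during the Salsalate treatment withdrew from the study due to dizziness" or tinnitus.
- **A trial of 108 patients with type 2 diabetes** on placebo or 3.0-4.0 g/day for 14 weeks: one tinnitus withdrawal is described, and three patients who needed a dose reduction completed. Total attrition is not given.
- **A small type 2 diabetes study:** no side effects at 3.0 g/day for 2 weeks, and no withdrawals described among a further 17 patients on 3-4 g/day for 4 weeks.

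Section VII.E.6 gives this trial's regimen as 3000 mg/day for 28-35 days.

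**The concern.** A conservative attrition rate should sit at or near the unfavourable end of the available evidence. The largest study cited is at about this trial's daily dose and over a shorter course, and its discontinuation rate is above the top of the assumed range. The arm size leaves nothing in reserve if the rate is exceeded.

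The plan also applies one rate to both arms, although the reasons it reports for stopping salsalate are mainly side effects of the drug. If losses follow that pattern, they will fall mainly on salsalate.

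At stake is the accuracy of the planning statement. A reader of XI.2 would take it that 16 salsalate completers and about 80% power are protected by a cautious allowance.

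**Working it through.** **Inputs.** From XI.2: d = 1.06, alpha 0.05, power 80%, 16 per group, 15-20% attrition, 20 and 10 randomized. Sidedness is not stated, so two-sided is assumed. From VIII.1: 234 of 782, 3 of 20 and 2 of 17. Power is for a two-sample t-test on the pre-to-post change (noncentral t), which is equivalent to the treatment-by-time interaction in XI.1 when there are two time points.

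**Step 1: reproduce the plan's figures.** At d = 1.06 and 80% power, the normal approximation gives 14 per group and the t-test 15. With d = 1.0, read directly from -1.0 ± 1.0, they give 16 and 17. The stated 16 is therefore reasonable. Inflating for loss, 16/0.85 = 18.8, rounded up to 19, and 16/0.80 = 20. The salsalate arm of 20 is the 20% case exactly. The placebo arm of 10 does not follow from 16 per group at any attrition rate.

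**Step 2: rates in the cited studies.** 234/782 = 29.9%; 3/20 = 15%; 2/17 = 11.8%. In the 782-patient study the named side effects alone (GI, tinnitus, dizziness) sum to 13.2 + 6.7 + 1.7 = 21.6%, before 8.5% for other reasons.

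**Step 3: salsalate completers out of 20.** Expected number = 20 × (1 - rate). The chance of fewer than 16 is binomial.

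| Loss on salsalate | Expected completers | P(fewer than 16) |
|---|---|---|
| 11.8% | 17.6 | 0.08 |
| 15% | 17 | 0.17 |
| 20% | 16 | 0.37 |
| 30% | 14 | 0.76 |

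To expect 16 completers at 30% loss would take 16/0.70 = 22.9, so 23 randomized to salsalate.

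**Step 4: power at d = 1.06.** Placebo completers at 15-20% loss are 10 × 0.85 = 8.5 to 10 × 0.80 = 8, so 8 or 9.

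| Salsalate v placebo | Situation | Power |
|---|---|---|
| 16 v 16 | as sized | 83% |
| 20 v 10 | no loss | 75% |
| 17 v 9 | about 15% in both arms | 69% |
| 16 v 8 | 20% in both arms | 65% |
| 14 v 9 | 30% salsalate, about 15% placebo | 66% |
| 14 v 8 | 30% salsalate, 20% placebo | 62% |
| 14 v 7 | 30% in both arms | 58% |

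**Step 5: separate the two causes.** Going from 16 v 16 to 16 v 8 costs 82.7 - 64.8 = 17.9 points, all from the placebo arm. Going from 16 to 14 salsalate completers with placebo held fixed costs 64.8 - 62.4 = 2.4 points (8 placebo) or 68.3 - 65.8 = 2.5 points (9 placebo). Measured from 17 completers it is 3.4 to 3.6 points.

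**The case against.** The strongest reply is that 30% does not transfer to this trial. It comes from arthritis patients, and GI effects are its largest component (13.2%). The exclusion criteria in VI.13 remove people with ulcers, dyspepsia, severe reflux or bleeding disorders, those taking NSAIDs or corticosteroids, and anyone judged unlikely to complete. Section VIII.2 provides for dose reduction before withdrawal. In every non-arthritis study in VIII.1 the withdrawal described is 15% or less, and the two highest of those figures come from doses above 3000 mg/day. On that evidence 15-20% is a defensible central allowance. This stands, and it is why 30% belongs at the upper end of a range.

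The second reply is that the 30% counts people who stopped the drug, who are lost to analysis only if Visits 6 and 7 are missed. That also stands in principle, but the plan gives little protection. VII.E.1.c and VIII.2 describe adverse events leading to withdrawal from the study, VII.E.7 plans no recontact of subjects lost to follow-up, and XI.1 names no analysis set and no handling of missing post-treatment data. The 14 completers are therefore an assumption, and the plan does not exclude it.

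A reader might go further and infer that XI.2 contains an arithmetic error, that 30% is the loss to expect, or that attrition is what takes power below 80%. The documents support none of these. The step from 16 to 20 is correct at 20% loss. The evidence on 30% is mixed, as above. Power is already 75% with no loss at all, and 14 v 9 (66%) is no worse than 16 v 8 (65%). The 58% figure requires 30% loss on placebo as well, which does not fit losses driven by the drug.

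**Conclusion.** The point holds in a limited form. The attrition rate in XI.2 has no source and is not conservative against the plan's own largest study. The salsalate arm meets its 16 only on average at 20% loss, with a 37% chance of falling short there and 76% at 30%. A sensible range for salsalate from the cited studies is about 12-30%, with 30% as an upper sensitivity value.

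The effect on power is modest: about 2 to 3 points relative to 20% loss. The 20:10 design delivers 75% with no loss, about 65-69% at 15-20% loss, and about 62-66% at 30% salsalate loss with 8-9 placebo completers. Most of the shortfall from 80% comes from the placebo arm of 10.

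These figures assume d = 1.06, a two-sided 0.05 test, independent losses, and that a subject who stops the drug provides no post-treatment measurement. If such subjects attend Visits 6 and 7 and are analysed, fewer are lost. Because XI.2 presents the study as a basis for sizing a larger trial, an accurate statement of completers and power matters more than reaching 80% here.

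**What to change.** In XI.2:

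1. Drop the word conservative and give attrition separately for each arm, with sources: salsalate about 12-30%, citing the studies in VIII.1 and marking 30% as the upper sensitivity value; placebo with its own stated rate.
2. Restate expected salsalate completers as about 14-17 of 20.
3. Replace the implied 80% with the power of the 20:10 design at d = 1.06, stating the two-sided 0.05 test: 75% with no loss, about 65-69% at 15-20% loss, about 62-66% at 30% salsalate loss with 8-9 placebo completers.
4. Say that most of the shortfall comes from the placebo arm of 10 and that the higher salsalate loss adds only about 2-3 points.

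It would help to state in XI.1 whether subjects who stop the drug are still measured and analysed, since that decides how much discontinuation becomes attrition.

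The cost is wording and one recalculation. Enrolment does not change; the stated power becomes less favourable.
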